2.6 Primary Endpoints

2.6.1 Primary Effectiveness Endpoint

The primary effectiveness endpoint of the study is an effectiveness measure based on Target Lesion Primary Patency (TLPP) through 6-months post index procedure.

2.6.2 Primary Effectiveness Endpoint Hypothesis Test

The primary effectiveness endpoint is TLPP through 6-months. Objective: To assess if the 6 month TLPP for the COVERA™ Vascular Covered Stent is greater than the effectiveness PG.

The primary effectiveness endpoint will be evaluated by the following hypothesis:

H₀: The proportion of subjects in the study device treatment group (P_{CE}) with TLPP through 6 month post index procedure is less than or equal to that of the effectiveness PG of 40%.

H₁: The proportion of subjects in the study device treatment group (P_{CE}) with TLPP through 6 month post index procedure is greater than that of the effectiveness PG of 40%.

That is:

H₀: $P_{CE} \leq 40\%$,

H₁: $P_{CE} > 40\%$,

Rejection of the null hypothesis will signify that the 6 month TLPP of the COVERA™ Vascular Covered Stent is greater than the effectiveness PG of 40%.

A one sided p-value will be derived based on an exact binomial test. The study device will be considered to have achieved the primary effectiveness objective if the one-sided p-value is less than 0.05. Or equivalently, the lower limit of the one-sided 95% confidence limit based on exact method is greater than 40%.

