2.2 Analysis populations

The analysis populations will be defined as follows for this study:

- The ITT population will consist of all subjects that have met all eligibility criteria, undergone successful PTA of the target lesion, and into which the COVERA™ Vascular Covered Stent System is introduced (i.e. the delivery system enters the subject's body).

Subjects who do not receive the study device, but into which the COVERA™ Vascular Covered Stent System was introduced, will be included in the ITT population. Subjects who require additional treatment modalities will be included in the ITT population.

- The Modified ITT (MITT) population will consist of any subjects in the ITT population who are treated with the COVERA™ Vascular Covered Stent (following PTA).
- A Per-Protocol (PP) population may be created if there are subjects who have any major protocol deviations. The PP population will consist of any subjects in the MITT population who do not have any major protocol deviation. The protocol deviations that are considered to have a "major" grade will be defined a priori in the analysis plan.

All analyses including the primary analyses will be primarily based on the MITT population. Key safety analysis will be performed based on ITT population as well. PP analyses may also be performed for the primary endpoints. They will only serve as sensitivity analyses for the primary analyses which are based on the MITT population.

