2.4 Handling of Missing Data

Study endpoints may be missing due to withdrawal of consent, Investigator's decision, LTF and subject death. It is important to minimize missing data by all means and always record the reason for missing. Missing data will be handled as described subsequently.

As a sensitivity analysis, the primary effectiveness and safety endpoints will also be analyzed using survival analysis techniques. In survival analyses, unobserved endpoints are a standard part of the analysis; they are known as "censored observations". As long as the censoring is unrelated to the treatment, this method of handling missing endpoints produces unbiased estimates of the freedom-from-event rates. For both primary endpoints, the reason for the censoring of all subjects with missing endpoints will be reported. If there is any indication that the censoring is related to the study intervention, a worst-case analysis may be performed for each primary endpoint, in addition to the standard analysis. In a worst-case analysis, an event will be assumed to have occurred at the time the subject was censored for all such subjects.

In addition, regardless of whether missing data are related to the study intervention, a tipping-point analysis will also be performed, in which assumptions about missing data are varied from worst-case to best-case to examine at what point the missing data would alter the results of the analysis.

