2.5 Sample Size Estimation

The sample size calculation assumes the following:

- 1) Primary Effectiveness Endpoint – TLPP at 6 months performance goal.
 - Assumptions:
 - The COVERA™ Vascular Covered Stent composite freedom from event rate is estimated at 55%;
 - The PG is set at 40%;
 - Attrition (drop-out) rate (by 6 months) = 15%;
 - The Type 1 error, $\alpha = 0.05$ (one-sided); and
 - The Type 2 error, $\beta = 0.10$ (Power = $1 - \beta = 90\%$).
 - Sample Size:
 - 109 treated subjects [93 evaluable] will give 90% power with one-sided type I error =0.05.
- 2) Primary Safety Endpoint – Safety at 30 days:
 - Assumptions:
 - The primary safety rate through 30 days in the study device treated subjects is 98%;
 - The PG is set at 88%;

- Attrition rate (by day 30) = 5%; and
- The Type 1 error, $\alpha = 0.05$ (one-sided).
- Sample Size:
 - 109 treated subjects [104 evaluable] will give 99% power with one-sided type I error =0.05.

Hence, the sample size of 109 subjects will provide approximately $(99\%)*(90\%)=89\%$ power for the both primary effectiveness and primary safety endpoint.

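### The exact binomial test of 6-month patency has no stated rule for counting early leavers, and no counting rule examined that avoids crediting them as patent gives the stated 90% power

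*Combined protocol and SAP*

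**What the plan says.** Section 2.6.2 tests whether the proportion with 6-month TLPP exceeds a performance goal of 40%: "A one sided p-value will be derived based on an exact binomial test". Success requires a one-sided p-value below 0.05, or equivalently an exact one-sided 95% lower limit above 40%.

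Section 2.2 sets the population: "All analyses including the primary analyses will be primarily based on the MITT population". MITT means the subjects actually treated with the device, planned as 109.

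Section 2.5 assumes a true rate of 55% and 15% attrition by 6 months, and concludes: "109 treated subjects [93 evaluable] will give 90% power with one-sided type I error =0.05". It does not define evaluable. It multiplies 90% by 99% for safety to reach about 89% for both endpoints.

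Section 2.4 announces a rule: "Missing data will be handled as described subsequently". Three items follow:
- "As a sensitivity analysis, the primary effectiveness and safety endpoints will also be analyzed using survival analysis techniques"
- if censoring appears related to the intervention, "a worst-case analysis may be performed for each primary endpoint, in addition to the standard analysis"
- in all cases, "a tipping-point analysis will also be performed"

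**The concern.** A binomial test needs a numerator and a denominator. Section 2.2 points to all treated subjects and section 2.5 to 93 of them. None of the analyses in section 2.4 defines the count for the primary test. A subject who leaves at month 3 with a patent lesion could be excluded or counted as a failure. A subject whose lesion failed at month 2 and who left at month 4 could be kept as a failure or excluded as a non-completer.

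These choices are not equivalent. If failures count whenever seen but successes count only after six full months, patency is understated even when drop-out is unrelated to outcome. If only completers count, independent drop-out causes no bias, but failures already observed are thrown away. In a single-arm study, a rule settled after outcomes are known could decide whether the goal is met.

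**Working it through.** **Inputs.** From sections 2.5 and 2.6.2: goal 40%, true rate 55%, one-sided alpha 0.05, 109 treated, 93 evaluable, 15% attrition. Assumed, because the documents give no drop-out timing: drop-out is independent of failure. Constant hazards are the base case, and other timings show the range.

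**1. The plan's own figure.** Normal approximation: n = [(1.645·√(0.40·0.60) + 1.282·√(0.55·0.45)) / 0.15]² ≈ 92.6, so 93, with power 90.1% at 93. Also 109 × 0.85 = 92.65. The stated 90% is therefore a normal-approximation figure.

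**2. The test actually named.** For n = 93, the smallest k with P(X ≥ k | 93, 0.40) < 0.05 is 46. Attained size is 0.0404, and power at 55% is 88.0%. For safety at n = 104, k = 98 and power is 99.5%. Joint power, using the plan's multiplication, is 0.8804 × 0.995 = 87.6%, not 89%. This gap comes from the discreteness of the exact test, not from the missing rule.

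**3. Counting rules, 109 treated, true patency 55%.** Scale time so that 6 months = 1. Failure hazard λ = −ln 0.55 = 0.598; drop-out hazard μ = −ln 0.85 = 0.163.

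- Patent and still followed at 6 months: 0.55 × 0.85 = 0.4675.
- Failure observed before leaving: λ/(λ+μ) × (1 − 0.4675) = 0.4187.
- Left while patent: 1 − 0.4675 − 0.4187 = 0.1138.

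Power is averaged over the random denominator, with k recomputed for each n.

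| Rule | Expected estimate | Power |
|---|---|---|
| Completers only, all leavers excluded | 0.4675/0.85 = 55.0% | 87.8%, at any timing |
| Observed failures kept, patent leavers dropped | 0.4675/0.8862 = 52.8% | 78.4% |
| All 109, leavers counted as failures (k = 53) | 46.75% | 38.3% |

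For the second rule:
- If everyone leaves just before 6 months, the estimate is 0.4675/0.9175 = 51.0% and power 68%. If everyone leaves at the start, power is 88%.
- Under constant hazards, 10% drop-out gives 84% power and 20% gives 71%.
- Mean n is 109 × 0.8862 = 96.6. If instead 15% of subjects leave while patent, so that 93 remain on average, the estimate is 52.0% and power 72%.
- Type I error at a true 40% is about 1.4% under constant hazards.

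**4. Kaplan-Meier on all 109.** Success means that the one-sided 95% lower limit (Greenwood variance, log-log scale) exceeds 40%. Simulation under constant hazards gives a mean estimate of 55.0%, power about 90% and type I error about 4.5%. Across the failure and drop-out timings tried, power is 88% to 93% and type I error 4.1% to 4.8%. On the same simulated constant-hazards trials, Kaplan-Meier passes where the second rule fails in about 12%; the reverse occurs in under 0.1%.

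**5. One data set, two answers.** Take 50 failures and 12 patent leavers, evenly spread, with 47 patent at 6 months. Second rule: 47/97 = 48.5%, p = 0.056, exact lower limit 39.7%, fails. Kaplan-Meier: 50.7%, lower limit 42.2%, passes.

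**6. Safety.** Section 2.6.4 has the same gap. With 5% attrition and event-free leavers dropped, the expected rate is 97.95% against 98% and power stays at 99.5%. The matter is confined to effectiveness.

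**The case against.** The strongest reply is that no bias has been shown, only that one possible rule would cause it. The completers-only count fits section 2.5 best, since 109 × 0.85 is about 93, and under independent drop-out it is unbiased with about 88% power. This stands. A reader might infer that the planned analysis understates patency and has 78% power; the documents do not support that, because they do not choose that rule or give drop-out timing. The completers-only rule has its own cost: it discards observed failures among leavers.

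A reader might also infer that the gap lets an ineffective device succeed. Counting leavers as patent would raise type I error to about 19% under constant hazards, but no passage suggests doing so. Dropping patent leavers while keeping failures is conservative.

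Section 2.4 already requires a survival analysis and a tipping-point analysis, so a reader of the results would see how far leavers matter. That also stands, but neither defines the primary count.

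A rule may sit in text not supplied. Section 2.6.1 names TLPP without its detailed definition, and section 2.2 refers to an a priori list of major deviations that the supplied plan does not contain. This limits confidence.

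Finally, one sentence stating the rule would close the gap, so replacing the test is a preference. That is fair, and it is why the fix offers both routes.

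**Conclusion.** The point holds as a specification gap that should be fixed, with medium confidence. The supplied text does not say how the planned 15% of early leavers are counted in the only test that decides effectiveness. Under the plan's own 55% and 109 treated, with independent drop-out, power ranges from about 38% to about 88% across the three rules. The 78% is an illustration resting on one rule and constant hazards, not a property of the plan. Under that rule, the harm is a missed success and a patency rate reported too low, not a false success.

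Separately, and whatever the rule, the 90% in section 2.5 does not belong to the exact test at 93 evaluable: that figure is 88.0%, or 87.6% jointly with safety.

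**What to change.** **Preferred.** In section 2.6.2, make the Kaplan-Meier estimate of 6-month TLPP in all MITT subjects the primary analysis, with success if the one-sided 95% lower limit (Greenwood variance, log-log scale) exceeds 40%. State when and why a subject is censored, including at death, which section 2.4 lists as a reason for missing endpoints. Keep the exact binomial test with a stated denominator, the worst-case analysis and the tipping-point analysis as sensitivity analyses.

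This needs wording changes in sections 2.6.2 and 2.5, and no new data or subjects. It uses every observed failure and all partial follow-up. Its downsides are:
- The test is asymptotic rather than exact, and 90% power is not assured at every drop-out timing.
- It needs independent censoring. Section 2.4 says that survival analysis "produces unbiased estimates of the freedom-from-event rates" only when censoring is unrelated to treatment; the worst-case and tipping-point analyses should probe this.
- The documents do not say whether the 40% goal rests on survival estimates or simple proportions, so comparability should be checked.

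**If the exact binomial stays primary.** State the early-leaver rule and the denominator in section 2.6.2, and do not count subjects patent at last contact as patent at 6 months. Restate the power in section 2.5 to match: at most about 88% for effectiveness and 87.6% jointly with 93 evaluable. If observed failures are kept and patent leavers dropped, it is about 78% for each under constant hazards (joint 0.784 × 0.995 = 78.0%).

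If the full TLPP definition or other analysis-plan text already holds a counting rule, cite it in section 2.6.2 and align section 2.5 with it.

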2.6.3 Primary Safety Endpoint

The primary safety endpoint is a safety measure based on safety through 30 days post index procedure.

2.6.4 Primary Safety Endpoint Hypothesis Test

The primary safety endpoint is safety through 30 days. Objective: To assess if the 30-day primary safety rate for the study device is greater than the safety PG:

H_0 : The proportion of subjects in the study device treatment group (P_{CS}) free from safety events in the primary safety endpoint is less than or equal to the safety PG of 88%.

H_1 : The proportion of subjects in the study device treatment group (P_{CS}) free from safety events in the primary safety endpoint is greater than the safety PG of 88%.

That is:

H_0 : $P_{CS} \leq 88\%$,

H_1 : $P_{CS} > 88\%$,

Rejection of the null hypothesis will signify that the 30 day safety of the COVERA™ Vascular Covered Stent is greater than the safety PG of 88%.

A one sided p-value will be derived based on an exact binomial test. The study device will be considered to have achieved the primary safety objective if the one-sided p-value is less than 0.05. Or equivalently, the lower limit of the one-sided 95% confidence limit based on exact method is greater than 88%.

2.7 Evaluation of Secondary Endpoints

The following secondary endpoints will be summarized with descriptive statistics (without formal statistical hypothesis testing) using the MITT population. For categorical variables, summary statistics will include frequency counts and percentages. For continuous variables, summary statistics will include mean, standard deviation, minimum, median, and maximum.

- TLPP through 30 days, 90 days, 12 months, 18 months, and 24 months.
- ACPP through 30 days, 90 days, 6 months, 12 months, 18 months, and 24 months.
- Rate of device and procedure related AEs involving the AV access circuit through 90 days, 6 months, 12 months, 18 months, and 24 months.

- Total Number of AV Access Circuit Reinterventions through 30 days, 90 days, 6 months, 12 months, 18 months, and 24 months.
- Total Number of Target Lesion Reinterventions through 30 days, 90 days, 6 months, 12 months, 18 months, and 24 months.
- IPF evaluated at 30 days, 90 days, 6 months, 12 months, 18 months, and 24 months follow-up.
- IPF-T evaluated at 30 days, 90 days, 6 months, 12 months, 18 months, and 24 months.
- Secondary Patency evaluated through 30 days, 90 days, 6 months, 12 months, 18 months, and 24 months.
- Acute Technical Success.
- Acute Procedure Success (Anatomic and Clinical Success).

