Study Device:	
The COVERA™ Vascular Covered Stent is a highly flexible self-expanding endoprosthesis comprised of expanded polytetrafluoroethylene (ePTFE) encapsulating a nitinol (nickel-titanium alloy) stent framework. The inner lumen of the stent graft (blood contacting surface) is carbon impregnated.
 
The COVERA™ Vascular Covered Stent is available in a straight and a flared configuration. Devices will come on either an 8F or 9F system.
 
Table 1: COVERA™ Vascular Covered Stent Sizes
 
  
 Covered Stent Outer Diameter (mm)	Covered Stent Length (mm)	Endovascular System Length (cm)	
 
 30*	40	60	80	100	
   
 6	✓	✓	✓	✓	✓	80 and 120	
 
 7	✓	✓	✓	✓	✓	
 
 8	✓	✓	✓	✓	✓	
 
 9	✓	✓	✓	✓	✓	
 
 10	✓	✓	✓	✓	✓	
  
 
* Note: only the straight configuration of the implant is available in 30mm length.
	Covered Stent Outer Diameter (mm)	Covered Stent Length (mm)					Endovascular System Length (cm)	30*	40	60	80	100	6	✓	✓	✓	✓	✓	80 and 120	7	✓	✓	✓	✓	✓	8	✓	✓	✓	✓	✓	9	✓	✓	✓	✓	✓	10	✓	✓	✓	✓	✓
Covered Stent Outer Diameter (mm)	Covered Stent Length (mm)					Endovascular System Length (cm)																																						
	30*	40	60	80	100																																							
6	✓	✓	✓	✓	✓	80 and 120																																						
7	✓	✓	✓	✓	✓																																							
8	✓	✓	✓	✓	✓																																							
9	✓	✓	✓	✓	✓																																							
10	✓	✓	✓	✓	✓																																							
Enrollment:	Enrollment will continue until a total of one-hundred nine (109) subjects are treated with the COVERA™ Vascular Covered Stent. All subjects will be followed for 24 months post index procedure.																																											
Investigational Sites:	Up to 30 investigational sites in the United States (US).																																											

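### Acute Technical Success is summarized only in subjects treated with the stent, so an attempt that ends without a stent cannot count as a failure

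*Combined protocol and SAP*

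**What the plan says.** Section 2.7 sets one population for the whole list of secondary endpoints: "The following secondary endpoints will be summarized with descriptive statistics (without formal statistical hypothesis testing) using the MITT population". The list includes "Acute Technical Success" and, after it, Acute Procedure Success (anatomic and clinical). Neither has a population of its own.

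Section 2.2 defines the populations. Entry to ITT requires that eligibility is met, that angioplasty of the target lesion has succeeded, and that the delivery system has entered the body. On subjects left without a stent it says: "Subjects who do not receive the study device, but into which the" (device name) "System was introduced, will be included in the ITT population". The narrower set is defined thus: "The Modified ITT (MITT) population will consist of any subjects in the ITT population who are treated with the" covered stent.

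The same section sets the default, "All analyses including the primary analyses will be primarily based on the MITT population", and adds ITT only for key safety analysis. The Protocol Summary (section 1, Enrollment) fixes the size of the treated group: "Enrollment will continue until a total of one-hundred nine (109) subjects are treated".

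**The concern.** Technical success is the endpoint in which one would expect to see a delivery attempt that did not end with a stent in place. Under sections 2.2 and 2.7 together, the subject must already have been treated with the stent before being counted. Membership of the denominator then depends on part of the outcome being measured.

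MITT is easier to defend for patency, which describes the course of an implanted device. It suits technical success less well. Section 2.2 foresees the subject with the system introduced and no device received, and retains that subject in ITT, but section 2.7 does not use ITT for the one endpoint where the retention matters most.

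At stake is one descriptive rate. It could be reported as higher than the experience of all subjects in whom delivery was attempted.

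**Working it through.** **Inputs**

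- Population for Acute Technical Success: MITT (section 2.7).
- MITT: ITT subjects treated with the stent (section 2.2).
- ITT: also includes subjects with the system introduced and no device received (section 2.2).
- Treated subjects: 109 (section 1, Enrollment).
- *k*, the number of introduced-but-not-implanted subjects: not in the documents, so assumed.

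The plan states no technical success rate, so there is no figure of its own to reproduce.

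**Step 1: who is lost.** ITT minus MITT is exactly the group with the system introduced and no stent received. It adds 0 to the numerator and 0 to the denominator of the MITT rate, whatever *k* is. Because enrollment runs until 109 are treated, these subjects do not reduce the MITT denominator; it stays at 109.

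**Step 2: the highest possible rate.** If every treated subject is a success, MITT gives 109/109 = 100% for any *k*. ITT, with non-implants counted as not successful, gives at most 109/(109 + *k*):

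| Assumed *k* | Highest ITT rate | Gap from 100% (points) |
|---|---|---|
| 0 | 109/109 = 100% | 0 |
| 1 | 109/110 = 99.1% | 0.9 |
| 2 | 109/111 = 98.2% | 1.8 |
| 3 | 109/112 = 97.3% | 2.7 |

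**Step 3: with some failures among treated subjects.** If 107 of 109 are successes, MITT shows 98.2%. ITT gives 107/110 = 97.3% for *k* = 1 and 107/112 = 95.5% for *k* = 3, which is lower by 0.9 and 2.6 points.

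**Step 4: how likely is any loss?** Let *q* be an assumed chance that an attempt ends without a stent, independent between subjects. The chance of at least one before 109 are treated is 1 − (1 − *q*)^109, and the expected number is 109*q*/(1 − *q*):

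| Assumed *q* | Chance of at least one | Expected number | Chance of 5 or more |
|---|---|---|---|
| 0.5% | 42% | 0.5 | 0.03% |
| 1% | 67% | 1.1 | 0.6% |
| 2% | 89% | 2.2 | 7.7% |

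The last column is a negative binomial tail. A count of 5 would bring the highest ITT rate down to 109/114 = 95.6%, but on these assumptions that is a tail case. The expected counts point to a gap of roughly 0.5 to 2 points.

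**Step 5: Acute Procedure Success is different.** Every ITT subject has already had successful angioplasty, and section 2.2 keeps subjects who need additional treatment in ITT. A non-implanted subject might therefore meet an anatomic and clinical definition. Suppose 107 of 109 treated subjects succeed (98.17%) and *k* = 3. If all three non-implants meet the definition, ITT gives 110/112 = 98.21%, slightly higher than MITT. If none does, it gives 107/112 = 95.54%. The direction is not fixed.

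**The case against.** The strongest objection is that the available text does not define Acute Technical Success. If it is defined per deployed device, for example as accuracy of deployment, then an attempt with no deployment is outside the endpoint by design and nothing is lost. This stands as a condition on the conclusion. It does not remove the point, because no other definition can bring back subjects whom the population excludes.

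Second, section 2.2 gives no reasons for non-receipt. A system may be withdrawn for causes unrelated to the device, so counting every such subject as not successful is a conservative convention rather than a fact about the device. This also stands, and is why the reasons should be reported.

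Third, the default in section 2.2 is only that analyses are primarily in MITT, which leaves room for ITT supplements, and a reader given both population sizes can subtract one from the other. That is true, but the only ITT analysis named is key safety, section 2.7 names MITT without qualification, and the subtraction does not correct the reported rate.

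A reader might go further and infer that all delivery problems vanish from the rate. The documents do not support that. A poorly placed stent remains in MITT. The exclusion is by subject, so someone who receives a stent from a second system after a first fails is also in MITT, and whether the first failure counts depends on the definition.

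A reader might also infer that Acute Procedure Success is overstated in the same way. Step 5 of the working shows that this does not follow.

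**Conclusion.** The concern holds for Acute Technical Success, at low severity. As the plan is written, a subject in whom the system was introduced and no stent was received cannot count as a failure. Unless the endpoint is defined only per deployed device, such attempts make the reported rate too favourable.

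The size cannot be fixed from the documents. The illustration of 99.1% to 97.3% against a possible 100% rests on 1 to 3 assumed non-implants and on counting each as not successful. If there are none, the two rates coincide.

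It would be wrong to read this as a threat to the trial's main conclusions. The secondary endpoints carry no hypothesis test, so alpha, power and both primary comparisons with the performance goals are unaffected. No bias of known direction is shown for Acute Procedure Success.

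**What to change.** In section 2.7, state that Acute Technical Success is summarized in the ITT population already defined in section 2.2. Count introduced-but-not-implanted subjects as not successful, give their number and the reasons, and show the MITT rate as a supplement with both denominators. If the endpoint is in fact defined per deployed device, say so there and report the number of non-implants beside the rate.

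For Acute Procedure Success, do not score non-implants as failures by rule. At most, add an ITT rate scored by the endpoint's own definition.

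The cost is one or two sentences and one table column. Counting and describing the non-implants uses index-procedure information on subjects already in ITT and needs no added follow-up. The downside is a descriptive rate that may be slightly less favourable.

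### Section 2.7 reports patency through 24 months as counts and percentages, with no denominator at each time point, no rule for subjects lost earlier and no confidence interval

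*Combined protocol and SAP*

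**What the plan says.** Section 2.7 sets the method for all secondary endpoints: "The following secondary endpoints will be summarized with descriptive statistics (without formal statistical hypothesis testing) using the MITT population". Two kinds of summary follow. Continuous variables get means, medians and similar statistics. For the other kind, "For categorical variables, summary statistics will include frequency counts and percentages".

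Three of the listed endpoints are patency endpoints. TLPP is to be reported at five time points and ACPP at six, the last of them at two years in each case. The third is given as "Secondary Patency evaluated through 30 days, 90 days, 6 months, 12 months, 18 months, and 24 months".

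Section 2.4 deals with missing data. It opens generally ("Study endpoints may be missing due to withdrawal of consent", followed by Investigator's decision, loss to follow-up and death), but its method is narrower: "As a sensitivity analysis, the primary effectiveness and safety endpoints will also be analyzed using survival analysis techniques". Its reporting of censoring reasons and its worst-case analysis are likewise tied to the primary endpoints. Its tipping-point sentence names no endpoint and sets no estimator or denominator. Confidence limits appear only in sections 2.6.2 and 2.6.4, for the two primary tests.

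**The concern.** Patency through a time point is a time-to-event outcome, and some subjects will leave before the event or the time point. Naming MITT fixes who is in the analysis set. It does not say how a subject who leaves at month 9 with a patent lesion counts at month 24. Three simple conventions are open, and each is biased even when drop-out is independent of patency:

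- **Known status only** is too low. Failures among subjects who would later have been lost are kept, while patent subjects who are lost drop out of the denominator.
- **Lost counted as patent** is too high.
- **Patent over all MITT** is too low, because every lost subject counts as a failure.

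A crude percentage is unbiased under independent drop-out if it is taken among all subjects followed to the time point whether or not they had an event. The plan does not specify this.

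The 12- to 24-month results are the durability evidence beyond the 6-month primary endpoint, in a single-arm study. With no rule fixed, the choice of convention can be made after the data are seen.

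**Working it through.** **The plan's own figures.** Section 2.7 states none. Section 2.5 assumes 15% attrition by 6 months and 5% by day 30: 109 × 0.85 = 92.65 (stated as 93 evaluable) and 109 × 0.95 = 103.55 (stated as 104). These reproduce and are used below.

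**Inputs**
- From section 2.5: event-free rate 55% at 6 months; retention 0.95 at day 30 and 0.85 at 6 months.
- Assumed, because the plan is silent: true 24-month TLPP of 30% (range 9% to 40%, where 9% is 0.55⁴ = 0.0915), and attrition after month 6 as in cases A to C.
- Drop-out independent of patency; hazards constant within each interval.

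**Formulas.** Let S be true patency and G retention. For an interval starting at S₀ and G₀, with interval survival s and interval retention g, the observed failures are

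f = S₀ · G₀ · [ln s / (ln s + ln g)] · (1 − s·g), and F is the sum of f over intervals.

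Then known status only = S·G / (S·G + F); lost counted as patent = 1 − F; patent over all MITT = S·G.

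**Case A: 15% lost by month 6, none later, S(24) = 0.30**
- Months 0–6: s = 0.55, g = 0.85, so f = 0.7863 × 0.5325 = 0.4187.
- Months 6–24: s = 0.30/0.55 = 0.5455, g = 1, so f = 0.55 × 0.85 × 0.4545 = 0.2125.
- F = 0.6312; S·G = 0.30 × 0.85 = 0.255.
- Known status: 0.255 / 0.8862 = 28.8%. Lost as patent: 36.9%. All MITT: 25.5%.

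**Case B: loss continues at the month 1–6 rate**
- Hazard ln(0.95/0.85)/5 = 0.0222 per month, so G(24) = 0.570 (43% lost).
- F = 0.5919; S·G = 0.171. Results: 22.4%, 40.8%, 17.1%.

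**Case C: 15% lost in every 6 months**
- G(24) = 0.85⁴ = 0.522 (48% lost).
- F = 0.5910; S·G = 0.157. Results: 20.9%, 40.9%, 15.7%.

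The gap between the lowest and highest convention is 36.9 − 25.5 = 11.4 points in case A and 40.9 − 15.7 = 25.2 points in case C.

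**Bias in points over an assumed true 24-month TLPP of 9% to 40%**

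| Case | Known status only | Lost as patent | All MITT |
|---|---|---|---|
| A | −0.4 to −1.6 | +5.4 to +10.0 | −1.4 to −6.0 |
| C | −3.2 to −11.4 | +7.9 to +16.0 | −4.4 to −19.1 |

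**ACPP and Secondary Patency.** The plan gives no expected rate. With a constant event hazard to assumed 24-month rates, in the same column order:

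| Assumed true rate | Case A | Case C |
|---|---|---|
| 15% | 14.5 / 24.8 / 12.8% | 10.2 / 31.4 / 7.8% |
| 80% | 79.6 / 82.6 / 68.0% | 73.7 / 85.1 / 41.8% |

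**Sensitivity to the event path.** With one constant event hazard to 24 months instead of 55% at month 6, a true 30% gives 28.0 / 34.4 / 25.5% at 15% lost by 24 months and 22.2 / 45.2 / 15.7% at 47.8% lost. The directions are unchanged.

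**Precision.** In 4,000 simulated trials of 109 subjects with S(24) = 0.30, the Kaplan-Meier mean was 0.301 in case A and 0.300 in case C (SD 4.7 and 5.2 points). The percentage among all subjects followed to 24 months had means of 0.301 and 0.299 (SD 4.7 and 6.2 points). With complete data, 33/109 (30.3%) has an exact 95% interval of 21.8% to 39.8%.

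**The case against.** The strongest reply is that this is a small matter of wording. The endpoints are descriptive and no decision rule uses them. A plain reading of section 2.7 makes all MITT the denominator, and nothing in the plan suggests counting lost subjects as patent. The list of summaries need not be exhaustive, so Kaplan-Meier estimates and intervals are not ruled out. With only the documented 15% loss, the known-status bias at a true 30% is 1.2 points, well inside sampling error. The larger biases need attrition and patency values that the plan does not give. Finally, Kaplan-Meier is not the only sound repair, and it too needs independent censoring, which is open to question when death is among the reasons for missing data.

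Much of this stands. The endpoints are descriptive, the later attrition is assumed, the known-status bias is small if nobody is lost after month 6, and a percentage among all subjects followed to the time point would also be unbiased under independent drop-out. But the all-MITT reading does not rescue the plan: it gives 25.5% against a true 30% with no more than the documented loss. A list that may be non-exhaustive does not commit anyone to a particular estimate. The tipping-point sentence in section 2.4 supplies neither an estimator nor a denominator. The question about death is a reason to write the rule down.

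**Conclusion.** The concern holds. As written, section 2.7 does not determine the 24-month patency figures, and the natural readings of a crude percentage are biased under independent drop-out. At an assumed true TLPP of 30%, the three conventions span about 11 points if loss stops at the 15% of section 2.5, and about 25 points if loss continues at 15% per 6 months. The sizes rest on assumed 24-month patency, assumed later attrition and piecewise-constant hazards; the directions of bias do not depend on the particular values chosen. The omitted interval matters as well, since one based on 109 subjects is about 18 points wide (39.8 − 21.8).

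The plan already accepts the principle for its primary endpoints: "As long as the censoring is unrelated to the treatment, this method of handling missing endpoints produces unbiased estimates of the freedom-from-event rates". It does not carry that method to the later time points, where cumulative loss can only be equal or greater. The primary conclusions and sample size are unaffected, so this is a change that should be made, not one on which the trial depends.

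**What to change.** In section 2.7, report TLPP, ACPP and Secondary Patency at each time point as Kaplan-Meier estimates with 95% confidence intervals and numbers at risk, beside the counts. For each reason for missing data listed in section 2.4 (withdrawal, Investigator's decision, loss to follow-up, death), state whether the subject is censored or counted as an event. If a percentage is also shown, state its denominator at each time point.

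The cost is SAP wording and minor extra programming on event and last-contact dates, which the survival sensitivity analyses in section 2.4 already need. Sample size, visits and the primary tests do not change.
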